8.6. Concomitant Medications

All concomitant medication use (with the exception of IV fluids, vitamins, and nutritional or electrolyte supplements other than oral magnesium) will be captured through Week 16.

BCV was a direct in vitro inhibitor of cytochrome (CYP)3A, 2B6 and 2C8 (IC_{50} 5 to 17 μ M); and CYP1A2, 2C9, 2C19, and 2D6 (IC_{50} 22 to 28 μ M) in human liver microsomes.

No significant induction of CYP enzymes 1A2, 2B6, and 3A by BCV was observed after incubation with freshly isolated and cultured human hepatocytes. Inhibition of the drug transporters P-glycoprotein (P-gp, IC_{50} 20 μ M), breast cancer resistance protein (IC_{50} 11 μ M), and OATP1B1 (IC_{50} 21 μ M) by BCV was observed in vitro.

BCV is not an inhibitor of either CYP3A or P-gp in vivo. Co-administration of oral BCV 200 mg with IV and oral midazolam, a sensitive CYP3A substrate, did not alter plasma midazolam PK. Co-administration of oral BCV 200 mg with oral dabigatran etexilate 150 mg, a sensitive P-gp substrate, did not increase plasma total dabigatran exposure. Therefore, BCV is not expected to alter concentrations of other compounds metabolized by CYP enzymes or other compounds transported by P-gp.

BCV was not a substrate for P-gp or breast cancer resistance protein; however, BCV was a substrate for OATP1B1 and OATP1B3.

Cyclosporine

Co-administration of cyclosporine (a potent OATP inhibitor) increased plasma BCV exposure. Based on population PK analysis, plasma BCV exposure (AUC_{ss}) is increased by approximately 43% when cyclosporine is co-administered. The magnitude of PK interaction identified in a drug-drug interaction study (CMX001-120) conducted in healthy volunteers (average 4.74-fold increase in plasma BCV AUC_{inf}) was greater than estimated in virally-infected patients enrolled in BCV clinical studies based on a Population PK analysis. To adjust for the PK interaction observed in patients, subjects receiving concurrent cyclosporine in this study will receive a lower BCV dose (Table 6).

Analyses conducted with data from subjects enrolled in five clinical studies showed that the co-administration of cyclosporine and unadjusted BCV increased the odds of elevations of total bilirubin \geq Grade 2 and of moving to a higher hepatobiliary AE level (levels were “no AE,” “non-serious/ $<$ Grade 3,” and “serious/ \geq Grade 3”). BCV and cyclosporine had independent, not synergistic, effects on total bilirubin and hepatobiliary AEs in a safety exposure-response analysis.

Due to the overlap of BCV and cyclosporine safety profiles, subjects receiving BCV and cyclosporine should be closely monitored for hepatobiliary AEs and laboratory abnormalities, as specified in Section 8.3.2. Other immunosuppressant therapies (e.g., tacrolimus) should be considered, if clinically appropriate.

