Until a subject has achieved sufficient immune reconstitution, reactivation of latent virus from the gut may result in a subsequent episode of AdV viremia. Subjects who stop BCV therapy after achieving confirmed undetectable AdV viremia may re-initiate treatment with BCV if AdV viremia is subsequently confirmed at ≥ 1000 copies/mL by the designated central virology laboratory, unless precluded by the BCV toxicity management guidelines. For the purposes of re-initiating BCV therapy, "confirmed AdV viremia ≥ 1000 copies/mL" is defined as two consecutive results ≥ 1000 copies/mL from the designated central laboratory, with the second sample drawn at least 48 hours after the first sample. BCV dosing will be resumed at the same dose and dose frequency the subject was receiving when BCV therapy was stopped (i.e., if BCV dosing had been consolidated to once weekly [QW] administration for toxicity management purposes, the subject would resume at the QW dose).

Subjects who permanently discontinue BCV for toxicity reasons are not eligible to re-initiate BCV therapy.

Treatment with BCV may not be extended past Week 16 under this protocol. Therefore, investigators wishing to extend or re-initiate treatment with BCV for a subject after Week 16 will need to request access to the drug through the local named patient program (NPP) or other expanded access program, where available.

The duration of any therapy administered as part of SoC will be determined by local institutional practice. Subjects randomized to the SoC arm will be managed according to local institutional practice and guidelines and any relevant product labelling. To allow for a meaningful and interpretable comparison of safety and efficacy between treatment arms, subjects randomized to the SoC arm will NOT be eligible to receive BCV therapy prior to Week 16 post-randomization. After completion of the Week 16 assessment, subjects randomized to the SoC arm may be able to access BCV through the local NPP or other expanded access program, as described above.

All subjects will be followed for a period of 36 weeks post-randomization, regardless of treatment assignment, including SoC subjects who begin BCV treatment after Week 16 post-randomization.

Reference Therapy, Dosage and Mode of Administration:

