Stored blood (plasma) samples or extracted DNA will be used for AdV typing by PCR amplification and sequencing of the variable region of the hexon gene. Determination of baseline genotype will be carried out by PCR amplification and sequencing of the AdV DNA polymerase gene. Emergence of antiviral-resistant AdV due to virologic failure will be determined by genotyping the AdV polymerase gene from subjects where: (1) confirmed recurrence of AdV viremia ≥ 1000 copies/mL is noted subsequent to viral clearance; (2) confirmed increase in plasma AdV DNA by $\geq 1 \log_{10}$ after experiencing a $\geq 1 \log_{10}$ decrease from baseline, and (3) non-responders and/or subjects with detectable plasma AdV DNA at the last on-treatment measurement. Stored samples may also be used for AdV viremia/viral load assessments; additional resistance analyses based on newly available assays, including phenotyping for resistance and deep sequencing; and for retrospective analyses of other dsDNA virus viremia/viral loads. **No stored samples will be used for human genomic analyses.**

Changes in AdV-related disease signs and symptoms will be evaluated throughout the study.

Safety: Safety will be assessed through physical examination findings, vital signs measurements, and the collection of blood and urine samples for routine safety assessments (analyzed by the designated central safety laboratory), including hepatic and renal assessments, determined at periodic intervals through 36 weeks post-randomization. AEs will be recorded from the time of administration of the first dose of BCV or, for subjects randomized to SoC, from the date of randomization, until completion of the Week 16 assessment or premature discontinuation from the study. In addition, any study procedure-related AE that occurs prior to administration of the first dose of BCV (or randomization to SoC) will be recorded as an AE. After the Week 16 assessment, until completion of the Week 36 assessment, only serious adverse events (SAEs) will be recorded. Subjects will also complete electronic diaries (e-diaries) collecting diarrhea symptoms on a daily basis (and date/time for each BCV dose and whether taken with food) through Week 16. Concomitant medication use will be recorded through Week 16.

Specific monitoring and BCV stopping criteria will be followed for targeted GI and hepatic abnormalities, as described below.

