5.3.2. Other Secondary Efficacy Endpoints

- Time to all-cause mortality through Week 16
- Incidence of and time to all-cause mortality through Week 36
- Incidence of and time to non-relapse mortality through Weeks 16 and 36
- Incidence of and time to AdV-associated mortality through Weeks 16 and 36, where mortality is assessed by a blinded EAC
- Proportion of subjects with undetectable AdV viremia at Weeks 2, 4, 6, 12, and 16
- Proportion of subjects with $\geq 2\text{-log}_{10}$ decline from baseline or undetectable AdV viremia at Weeks 2, 4, 6, 12, and 16
- Proportion of subjects with $\geq 1\text{-log}_{10}$ decline from baseline or undetectable AdV viremia at Weeks 2, 4, 6, 12, and 16
- AAUC at Weeks 2, 4, 6, and 12
- Incidence of and time to first confirmed undetectable AdV viremia
- Incidence of and time to virologic relapse (subsequent confirmed AdV viremia ≥ 1000 copies/mL) among subjects with confirmed clearance of AdV from plasma (overall; by AdV in urine, stool, and respiratory secretions at the time of first undetectable AdV viremia; and by T cell-mediated immune function [e.g., CD4+ cells $>$ or ≤ 50 cells/ μL] at the time of first undetectable AdV viremia)
- Maximum PELOD score through Week 16
- Number of days spent in the hospital through Week 16
- Number of days spent in the ICU through Week 16
- Emergence of AdV mutations associated with genotypic resistance and phenotypic resistance (the latter when possible) to BCV or CDV
- Incidence of and time to progression to probable or definitive AdV disease (among asymptomatic subjects at baseline)
- Incidence of and time to resolution of AdV clinical disease (among subjects with probable or definitive AdV disease at baseline)

- Primary model-based PK parameters, such as apparent clearance (CL/F), intercompartmental clearance (Q/F), volume of central compartment (V_c/F), volume of peripheral compartment (V_p/F), absorption rate constant (K_a), and lag time (T_{lag}), secondary PK parameters, such as C_{max} and area under the plasma concentration time curve at steady state (AUC_{ss}), and identification of covariates that influence these PK parameters
- Relationship between plasma BCV exposure, other covariates of interest, and
 - safety endpoints, including GI AEs, diarrhea, ALT, total bilirubin, and other safety events of interest
 - virologic endpoints including AAUC, AAUCMB, viral load change from baseline, and other virologic endpoints of interest,

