6.3. Number of Subjects

Approximately 141 pediatric subjects will be randomized between the two treatment arms in a 2:1 ratio to receive either BCV or SoC.

Table 5: Schedule of Study Assessments/Procedures

Assessment/Procedure	Screening ^a	Baseline ^b	Treatment Period ^c																Follow-up ^e	
			1	2	3	4	5*	6	7*	8	9*	10*	11*	12	13*	14*	15*	16	24*	36*
Study Week	-3 to -1	0	1	2	3	4	5*	6	7*	8	9*	10*	11*	12	13*	14*	15*	16	24*	36*
Planned Study Day	-21 to -1	1	8	15	22	29	36	43	50	57	64	71	78	85	92	99	106	113	169	253
Written informed consent ^d	X																			
Assess/review entry criteria	X	X																		
Assess/review medical history	X	X																		
Physical examination ^e	X	X				X				X				X					X	
HCT comorbidity ^f		X																		
PELOD score ^g		X	←----- X -----→																	
Urine pregnancy test ^h	X	X				X				X				X					X	
HIV, HBV, HCV tests ⁱ	X																			
Randomization		X																		
BCV ^j			←----- X -----→																	
SoC ^k			←----- X -----→																	
Height/length		X																		
Body weight ^l	X	X		X																
Plasma for real-time AdV and CMV ^m and storage for other virologic assessments ⁿ	X	X	X	X	X	X	X	X	X	X	X	X	X	X	X	X	X	X	X	X
Urine, stool and respiratory secretion sample for AdV assessment ^o		X				X		X		X				X					X	
Stool collection for storage (possible future virologic analyses) ^p		X	X	X	X	X	X	X	X	X	X	X	X	X	X	X	X	X		
Assess clinical signs and symptoms for AdV disease	X	X	X	X	X	X	X	X	X	X	X	X	X	X	X	X	X	X	X	X

Assessment/Procedure	Screening ^a	Baseline ^b	Treatment Period ^c																Follow-up ^e	
			1	2	3	4	5*	6	7*	8	9*	10*	11*	12	13*	14*	15*	16	24*	36*
Study Week	-3 to -1	0	1	2	3	4	5*	6	7*	8	9*	10*	11*	12	13*	14*	15*	16	24*	36*
Planned Study Day	-21 to -1	1	8	15	22	29	36	43	50	57	64	71	78	85	92	99	106	113	169	253
Clinical chemistry and hematology	X	X	X	X	X	X	X	X	X	X	X	X	X	X	X	X	X	X	X	X
Coagulation panel	X	X	X	X	X	X	X	X	X	X	X	X	X	X	X	X	X	X	X	X
Lymphocyte (CD4+/CD8+) subsets and other potential immunologic predictors of virologic response		X	X	X	X	X	X	X	X	X	X	X	X	X	X	X	X	X	X	X
Urinalysis	X	X				X				X				X				X		
Diarrhea symptoms assessment and review subject e-diary	X	X	X	X	X	X	X	X	X	X	X	X	X	X	X	X	X	X	X	
Perform drug accountability		X	X	X	X	X	X	X	X	X	X	X	X	X	X	X	X	X	X	
Clinical AE assessment ^d		X	X	X	X	X	X	X	X	X	X	X	X	X	X	X	X	X	X	X
Review and record all concurrent medications	X	X	X	X	X	X	X	X	X	X	X	X	X	X	X	X	X	X		

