8.4. Re-initiation of BCV Dosing for AdV Viremia

Subjects who stop BCV therapy due to confirmed undetectable AdV viremia may re-initiate treatment with BCV if AdV viremia is subsequently confirmed at ≥ 1000 copies/mL by the designated central virology laboratory. For the purposes of re-initiating BCV therapy, “confirmed viremia ≥ 1000 copies/mL” is defined as two consecutive results ≥ 1000 copies/mL from the designated central laboratory, with the second sample drawn at least 48 hours after the first sample. BCV dosing will be resumed at the same dose and dose frequency the subject was receiving when BCV therapy was stopped (e.g., if BCV dosing had been consolidated to QW administration for toxicity management purposes, the subject would resume at the QW dose). Subjects should be managed as per the toxicity monitoring and management criteria as outlined in Section 8.3.2.

Subjects who permanently discontinue BCV for toxicity reasons are not eligible to re-initiate BCV dosing.

8.5. Access to BCV after Week 16

Subjects randomized to the BCV arm may receive up to 16 weeks of therapy with BCV (through Week 16 post-randomization). Treatment with BCV may not be extended past Week 16 under this protocol. Therefore, investigators wishing to extend or re-initiate treatment with BCV for a subject after Week 16 will need to request access to the drug through the local NPP (or other expanded access program), where available. If applicable, approval for access to BCV through the NPP should be secured prior to the subject completing the Week 16 assessment to ensure continuity of care.

Subjects randomized to the SoC arm are not allowed to receive BCV during the 16-week treatment period, whether under this protocol or through an expanded access mechanism. After completion of the Week 16 assessment, investigators may request access to BCV through the local NPP (or other expanded access program), where available.

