11.7. Concomitant Medications

All medications taken by subjects will be assessed and recorded in the eCRF at each study visit through Week 16, as described in Section 8.6.

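### Anti-AdV treatment is not recorded after Week 16, when BCV opens to the SoC arm, so crossover behind the Week 36 mortality and late SAE results cannot be systematically identified or dated

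*Combined protocol and SAP*

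**What the plan says.** Four places set the same end to medication capture:

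- Section 8.6: concomitant medication "will be captured through Week 16".
- Synopsis: "Concomitant medication use will be recorded through Week 16".
- Section 11.7: "All medications taken by subjects will be assessed and recorded in the eCRF at each study visit through Week 16".
- Table 5: the row "Review and record all concurrent medications" is marked from screening to Week 16 and is blank at Weeks 24 and 36.

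Access to BCV opens at that point. The synopsis states: "After completion of the Week 16 assessment, subjects randomized to the SoC arm may be able to access BCV through the local NPP". Section 8.5 repeats this for the SoC arm ("After completion of the Week 16 assessment, investigators may request access to BCV through the local NPP") and lets investigators ask for extended or renewed BCV for subjects in the BCV arm by the same route, where it exists. The synopsis keeps everyone in follow-up to Week 36, "including SoC subjects who begin BCV treatment after Week 16 post-randomization", so crossover is foreseen.

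Outcomes continue past Week 16. Section 5.3.2 lists "Incidence of and time to all-cause mortality through Week 36", and also non-relapse and AdV-associated mortality at Week 36. Section 12.2 analyzes efficacy by randomized assignment. Section 12.6 presents safety by randomized arm, and Section 12.6.1 has a separate summary of SAEs that start after Week 16. Section 12 gives no rule for describing or handling BCV use after Week 16.

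**The concern.** Recording of treatment stops at the moment when treatment can change arm. If some SoC subjects start BCV after Week 16 and some BCV subjects restart it, a smaller mortality difference at Week 36 than at Week 16 has at least two explanations: the effect fades, or the arms have become more alike in treatment. With no drug names or dates, a reader of the trial report could not tell which, nor even learn how many subjects crossed over. In the same way, an SAE at Week 28 in an SoC subject taking BCV would appear under SoC, with BCV exposure known only if the SAE record happens to mention it.

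Section 4.3.8 applies this reasoning to crossover before Week 16: it says switching could harm interpretation of the efficacy comparisons and complicate attribution of SAEs and deaths. The plan blocks crossover for the first 16 weeks for that reason, but does not record it afterwards.

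**Working it through.** The plan states no figure on this point, so there is none to reproduce. The check has two parts: whether another route captures the data, and how large the gap is.

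**1. Other routes after Week 16**

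- *SAE records.* SAEs are recorded to Week 36 in both arms (Sections 11.9.1 and 11.9.6). Each record carries causality and action taken for BCV or another anti-AdV drug (Section 11.9.3), and suspect drugs go on the SAE form (Section 11.9.4). Death is an SAE (Section 11.9.2), so deaths should have such a record.
- *What these miss.* They miss subjects without an SAE, SAEs for which the drug is not suspected and no action is noted, and non-fatal AdV-related events, which Sections 11.9.1 and 11.9.2 exempt from reporting. No field described gives the start and stop dates of anti-AdV treatment.
- *BCV Registry.* Enrollment is optional (Section 6.6).
- *Named Patient Program.* Section 4.2.3 counts its recipients (1028), but no linkage to the trial database is described.

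**2. Length of the gap**

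(36 − 16)/36 = 20/36 = 55.6% of planned follow-up.

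**3. SoC subjects who could cross over**

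Inputs: 47 SoC subjects (synopsis) and expected SoC mortality of 20% to 30% at Week 16 (Section 12.4.1).

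- 47 × (1 − 0.30) = 32.9
- 47 × (1 − 0.20) = 37.6

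About 33 to 38 subjects.

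**4. Illustration of dilution (assumed inputs)**

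The documents give neither a crossover rate nor mortality after Week 16. Assume that, among Week 16 survivors, mortality from Week 16 to 36 is s = 15% on SoC and b = 10% on BCV, and that a share q of SoC survivors starts BCV at Week 16 and takes on the BCV risk at once. The SoC-arm risk is s − q(s − b) and the difference between arms is (1 − q)(s − b).

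| q | SoC-arm risk | Difference (points) |
|---|---|---|
| 0% | 15.00% | 5.00 |
| 25% | 13.75% | 3.75 |
| 50% | 12.50% | 2.50 |
| 75% | 11.25% | 1.25 |

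This covers only deaths after Week 16. The listed endpoint runs from randomization, so deaths before Week 16 damp the effect. As a second assumed case, take a hazard ratio of 0.60 throughout, SoC mortality of 25% by Week 16 and 15% of survivors thereafter, and a fraction f of later SoC follow-up spent on BCV. The SoC cumulative hazards are −ln(0.75) = 0.288 and −ln(0.85) = 0.163. The ratio through Week 36 is 0.60 × (0.288 + 0.163) / [0.288 + 0.163 × (1 − 0.4f)], which gives 0.62, 0.64 and 0.66 at f = 0.2, 0.4 and 0.6. Both cases credit the BCV arm with continuing benefit although study BCV ends by Week 16 at the latest, so they show direction and rough scale only.

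**The case against.** The strongest reply is that the plan is not blind after Week 16. Every SAE record names action taken and suspect drugs, deaths are SAEs even when AdV-related, and the adjudication committee reviews every death (Section 4.5.2). BCV access is on request and only where available, so crossover may be rare. Week 36 mortality is among the other secondary endpoints with no power claim, safety is generally not tested (Section 12.6), late SAEs are tabulated apart from the on-study period, and barring BCV until Week 16 was a deliberate way to protect the comparison that matters most. A detailed SAP was also to follow (Section 12).

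Much of this stands, and it limits what may be said. A reader might infer that crossover will certainly occur and be wholly invisible. The documents support neither: access is conditional, and some crossover will show in SAE and death records. A reader might also infer that the Week 36 comparison is invalid, or that crossover could reverse it. By randomized arm it is a valid treatment-policy comparison. Under the illustrations above, crossover to a beneficial drug moves the difference toward zero but not past it: (1 − q)(s − b) is never negative.

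The reply does not close the gap. The partial records depend on an SAE occurring and on what the investigator attributes to the drug, so they cannot give a count of crossovers or their dates. A later SAP can add analyses but cannot recover data that were not collected.

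**Conclusion.** The concern holds in a limited form. Week 36 all-cause, non-relapse and AdV-associated mortality, and SAEs starting after Week 16, may include crossover that the planned data cannot systematically identify or date. The gap spans 20 of 36 weeks and, at the plan's own mortality range, about 33 to 38 SoC subjects. Its effect on the results cannot be stated, because no crossover rate is given. The dilution figures rest entirely on assumed mortality, effect and crossover, and are modest when the endpoint is counted from randomization.

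The primary and key secondary endpoints, both at Week 16, are unaffected. What the trial would lose is the ability to report how much BCV was used after Week 16 in each arm and to examine whether it influenced the later results.

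**What to change.** Amend Sections 8.6 and 11.7, the matching synopsis sentence and Table 5 so that, in both arms, the eCRF records BCV, cidofovir and AdV-specific cell therapy given after Week 16, with drug and start and stop dates, at the existing Week 24 and Week 36 visits and at death. Full concomitant medication review need not be extended.

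Pre-specify three outputs, all labelled descriptive:

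- a summary of BCV use after Week 16 by randomized arm;
- SAEs starting after Week 16, tabulated by BCV exposure at onset;
- one simple supportive analysis of Week 36 mortality that accounts for BCV start in the SoC arm, for example by ending SoC follow-up at that date, with a note that subjects who start BCV may differ in prognosis.

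The analysis by randomized arm stays as planned. An inverse-probability-weighted analysis is not advised. With 33 to 38 SoC survivors, only two remaining visits to supply covariates and, at the assumed 15% later mortality, about 5 or 6 later SoC deaths (32.9 × 0.15 = 4.9; 37.6 × 0.15 = 5.6), the weights would be unstable.

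This is a cheap improvement: one short form at visits already planned. The downside is a small added workload for sites.

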8.6.1. Prohibited Medications

8.6.1.1. Prohibited Medications for Subjects Randomized to Receive BCV

The following medications are prohibited while subjects are receiving treatment with BCV.

Cidofovir (Vistide)

As CDV and BCV deliver the same active antiviral (CDV-PP), these two medications must not be administered concurrently. Subjects who are receiving IV CDV at randomization and who are randomized to the BCV arm should wait at least 48 hours after administration of the last CDV dose (dose-to-dose) before initiating treatment with BCV.

Ketoconazole (non-topical formulations) and Sesamin-containing Products

In vitro experiments have shown that BCV is a substrate of CYP4F2. No clinical drug-drug interaction studies have been completed with CYP4F2 inhibitors to-date; however, given the in vitro data, co-administration of BCV with the potent CYP4F2 inhibitor ketoconazole (non-topical formulations) and sesamin-containing products is contraindicated.

No interaction is expected with other azole antifungals, including voriconazole, fluconazole, or posaconazole, based on in vitro data demonstrating that these drugs do not inhibit CYP4F2 at relevant physiologic concentrations, providing therapeutic alternatives to treatment with ketoconazole.

